## List of abbreviations

AF Atrial fibrillation

AFEQT: Atrial Fibrillation Effect on Quality of Life

AAD: Antiarrhythmic drugs

CFAE: Complex Fractionated Atrial Electrograms

CTI: Cavoatrial Isthmus

DC: Direct Current

ECG: Electrocardiogram

LA: Left atrium

PAF: Paroxysmal atrial fibrillation

PsAF: Persistent atrial fibrillation

PV: Pulmonary Vein

PVI: Pulmonary Vein Isolation

QoL: Quality of Life

VOM: Vein of Marshall

Protocol overview	
Title	RE-ABLATION OF PERSISTENT ATRIAL FIBRILLATION: A RANDOMIZED STUDY, EVALUATING VEIN OF MARSHALL ETHANOL ABLATION IN COMBINATION WITH BLOCK OF MITRAL AND TRICUSPID ISTHMUSES AND DOME LINE
Acronym	Re-AF study
Study design	An investigator initiated, randomized, patient-assessor blinded multi-center trial
Participating centers	Department of Cardiology, Aarhus University Hospital Department of Cardiology, Karolinska University Hospital, Stockholm Department of Cardiology, Leiden University Medical Center
Hypotheses	Addition of Vein of Marshall ethanol ablation in combination with block of mitral and tricuspid isthmuses and dome line to standard pulmonary vein re-isolation improves quality of life and reduces recurrence of atrial arrhythmias as compared to standard pulmonary vein re-isolation alone in patients undergoing re-ablation for persistent atrial fibrillation.
Eligibility criteria	
Inclusion criteria:
 
 
• Previous pulmonary vein isolation for atrial fibrillation
 
• Indication for catheter ablation with at least two episodes of symptomatic PsAF during the last 12 months
 
• Age <math>\geq</math> 18 years
 
• Expected survival <math>\geq</math> 12 months
 
• Able to provide informed consent
 
 
Exclusion criteria:
 
 
• Previous extrapulmonary atrial ablation other than cavotricuspid isthmus line, roof- or dome line or posterior wall isolation/ablation
 
• Atypical atrial flutter in addition to atrial fibrillation
 
• Atrial fibrillation secondary to a transient abnormality
 
• Uncontrolled hypertension
 
• Acute coronary syndrome, cardiac surgery, or TIA/stroke within the last 3 months
 
• Planned cardiac surgery within 1 year
 
• Dialysis or severe renal failure
 
• Active substance or alcohol abuse (>14 units/week)
 

Randomization and conduct of the study	In a patient-assessor blinded, randomized multi-center study, consecutive patients undergoing re-ablation for persistent atrial fibrillation are randomized (1:1) to: 1) standard therapy including re-isolation of pulmonary veins (control group) or 2) re-isolation of pulmonary veins and vein of Marshall ethanol ablation in combination with block of mitral and tricuspid isthmuses and dome line (intervention group). Patients are followed with standard ECG at 3 months, with standard ECG, 5-days' ECG monitoring and quality of life assessment after 12 months, with standard ECG and quality of life assessment after 24 months, through patient files at 60 months after the ablation.
Primary endpoint	Change in AFEQT score between baseline and 12 months.
Safety endpoints	Peri- or postprocedural complications (vascular complication needing intervention, conduction disturbances requiring a pacemaker, gastroesophageal fistula, phrenic nerve damage, stroke or systemic embolism, pulmonary vein stenosis, cardiac tamponade, anaphylactic reaction, pericarditis and death).
Secondary endpoints	
 
• Freedom from documented atrial arrhythmia at a whole standard ECG recording (regardless of the estimated duration) or Holter/CIED (<math>\geq 24</math> hours) at 12 and 24 months and 5 years (after 3 months blanking period), on or off antiarrhythmic drugs (AAD).
 
• Freedom from documented persistent atrial arrhythmia at 12 and 24 months and 5 years (after 3 months blanking period), on or off AAD.
 
• Freedom from DC cardioverted atrial arrhythmia at 12 and 24 months and 5 years (after 3 months blanking period), on or off AAD.
 
• Number of DC-cardioversions (after 3 months blanking period) and sustained atrial arrhythmia episodes at 12 and 24 months and 5 years.
 
• Freedom from accepted chronic atrial fibrillation at 12 and 24 months and 5 years.
 
• Freedom from re-ablation procedure at 12 and 24 months and 5 years.
 
• Change in AFEQT score between baseline and 24 months and between baseline and 5 years.
 

Number of patients	180
Follow up time	12 months (primary endpoint) and 24 months and 60 months

## 1.0 Background

Atrial fibrillation (AF) is the most common sustained arrhythmia in adults with a lifetime risk of approximately 30%. AF significantly increases the risk of stroke, is associated with increased overall mortality and may impair quality of life. Treatments to effectively eliminate AF and maintain sinus rhythm may not only improve quality of life, but may even reduce mortality.

In patients with paroxysmal AF (PAF), AF has been found to be triggered by frequent ectopic atrial activity emerging from the pulmonary veins (PVs). Pulmonary vein isolation (PVI) has been developed to isolate the ectopic activity from initiating AF. PVI has proven efficient in patients with PAF with 1-year success rates up to 90%.

In patients with persistent AF (PsAF), data on a PV trigger-based initiation is not so clear, and the 1-year efficacy of pulmonary vein isolation only in this population is reported between 50-70% and significant lower as compared with patients with PAF. Furthermore, in patients having recurrence after PVI, a large proportion of patients with PsAF have isolated pulmonary veins at re-ablation. This indicates that patients with PsAF that have recurrence after PVI might benefit from ablation outside the pulmonary veins.

For some time, it has been assumed that in patients with PsAF there may be additive effect to PVI, by targeting the atrial substrate responsible for AF maintenance. However, the best method to characterize and target this so-called “substrate” remains elusive. The most commonly employed techniques for targeting the substrate used in the past were the creation of linear lesions across critical structures of the left atrium (LA), ablation of complex fractionated electrograms (CFAE), and targeting areas of low voltage detected by multipolar electroanatomical mapping.

The STAR AF II study showed that addition of either linear ablation or ablation of CFAE to PVI for PsAF did not offer any additional benefit over PVI alone. There was no significant difference in the results of the three strategies in terms of freedom from AF or any atrial arrhythmia. In fact, there seemed to be a weak trend towards better outcome with PVI alone. However, the STAR- AF II study included only de-novo procedures and in patients returning for re-do procedures, only 20% had isolated veins, indicating that durable block across the lines was achieved in a minority of this cohort.

With updated approaches and technologies, including introduction of pulsed-field ablation, the efficiency of creating durable isolation of PVs has significantly increased over the last years. While PVI alone still remains the standard for the first ablation in patients with PsAF, the PVs are found to be isolated in a higher proportion of patients referred for re-do ablation. This shows that in these patients, PVI alone is not sufficient and revive the relevance of investigating the significance of targeting substrate outside PVs.

The VENUS study demonstrated the benefit of vein of Marshall (VOM) ethanol ablation in de novo ablation of PsAF. Furthermore, preliminary results of the Marshall plan study suggest the benefit of VOM ethanol ablation in combination with block of mitral and tricuspid isthmus and dome line, also in de novo ablation of PsAF. Whether this strategy improves outcome in patients with PsAF undergoing re-ablation where the need for extrapulmonary ablation might be higher has not been tested in a randomized study We aim to investigate,

if the addition of VOM ethanol ablation in combination with block of mitral and tricuspid isthmuses and dome line to PV re-isolation will improve the results of re-ablation of PsAF.

## 2.0 Aim

The aim of this study is to investigate whether the addition of VOM ethanol ablation in combination with block of mitral and tricuspid isthmuses and dome line to standard PV re-isolation improves quality of life as compared to PV re-isolation alone, in patients who undergo re-ablation for PsAF.

### 2.1 Hypothesis

Addition of VOM ethanol ablation in combination with block of mitral and tricuspid isthmuses and dome line to standard PV re-isolation improves quality of life and reduces recurrence of atrial arrhythmias as compared to standard PV re-isolation alone in patients undergoing re-ablation for PsAF.

## 3.0 Methods

### 3.1 Study conduct

This is an investigator-initiated and investigator-sponsored multi-center trial at the Department of Cardiology Aarhus University Hospital, Department of Cardiology, Karolinska University Hospital, Stockholm and Department of Cardiology, Leiden University Medical Center. The study is conducted in accordance with the protocol, applicable regulatory requirements and the ethical principles of the Declaration of Helsinki.

### 3.2 Study design

This study is a prospective, patient and assessor blinded, 1:1 randomized superiority trial. Consecutive patients referred for re-ablation of symptomatic PsAF after previous PVI will be included. All preoperative procedures will be conducted according to the department's standard operational procedures for AF ablation. In all patients, an electro anatomical map (CARTO™, Biosense Webster, Diamond Bar, CA, or EnSite X™, Abbott Laboratories, Abbott Park, IL) of the LA with a multipolar mapping catheter (PENTARAY™ or OCTARAY™, Biosense Webster, Diamond Bar, CA, or Advisor™ HD Grid, Abbott Laboratories, Abbott Park, IL) will be constructed and reconnection of PVs will be assessed in sinus rhythm. If reconnection is present, re-PVI will be performed and confirmed with the multipolar mapping catheter. Patients in atrial fibrillation will undergo cardioversion to sinus rhythm prior to mapping. After mapping and confirming isolation of the PVs, patients will be randomized using the Redcap Database software to intervention or control. The intervention group will undergo VOM ethanol ablation including supplementary LA and coronary sinus ablation, if needed to achieve mitral isthmus block plus creation of dome line and cavotricuspid isthmus (CTI) block according to section 3.7. VOM ablation, mitral and CTI ablation and dome line will not be performed in control group and patients in control group will undergo no further ablation. The energy source used will be radiofrequency ablation or pulsed field ablation, at the discretion of the physician. However, radiofrequency should be preferred near coronary arteries. For dome line, focal PFA is preferred. All post-procedural work-up and follow-up will be the same for both randomization groups and assessment of outcomes will be performed by personnel blinded to randomization.

### 3.3 Definition of persistent atrial fibrillation

A standard 12-lead ECG recording or a single-lead ECG tracing of  $\geq 30$  s showing heart rhythm with no discernible repeating P waves and irregular RR intervals (when atrioventricular conduction is not impaired) is diagnostic of clinical AF. A high-rate episode detected by implanted device or wearable monitor, may be diagnostic of AF after inspection of the stored electrogram.

An episode of AF, continuously sustained beyond 7 days, including episodes terminated by cardioversion (drugs or electrical cardioversion) after  $\geq 7$  days, is regarded as PsAF.

### 3.4 Eligibility criteria

Consecutive patients are included on the following criteria:

#### 3.4.1 Inclusion criteria:

- Previous pulmonary vein isolation for atrial fibrillation
- Indication for catheter ablation with at least two episodes of symptomatic PsAF during the last 12 months during
- Previous PVI for atrial fibrillation
- Age  $\geq 18$  years
- Expected survival  $\geq 12$  months
- Able to provide informed consent

#### 3.4.2 Exclusion criteria:

- Previous extrapulmonary atrial ablation other than cavotricuspid isthmus line, roof- or dome-line or posterior wall isolation/ablation
- Atypical atrial flutter in addition to atrial fibrillation
- Atrial fibrillation secondary to a transient abnormality
- Uncontrolled hypertension
- Acute coronary syndrome, cardiac surgery, or TIA/stroke within the last 3 months
- Planned cardiac surgery within 1 year
- Dialysis or severe renal failure
- Active substance or alcohol abuse ( $>14$  units/week)

### 3.4 Power calculation

Assuming a 10-point difference in the change in AFEQT score between the intervention and control group with 90% power and a 5% significance level, assuming a standard deviation of 20 points (typical standard deviation for QoL in studies using the AFEQT questionnaire), a sample size of 168 patients will be required. With expected dropout during follow-up, 180 patients will be randomized in the study. The study will also be powered for the secondary endpoint (90% power and a 5% significance level, assuming 75% freedom of persistent atrial arrhythmia in the intervention group and 50% in the control group, a sample size of 148 patients is required).

### 3.5 Study endpoints

Primary endpoint:

- Change in AFEQT score between baseline and 12 months.

Secondary endpoints:

- Freedom from documented atrial arrhythmia at a whole standard ECG recording (regardless of the estimated duration) or Holter/CIED ( $\geq 24$  hours) at 12 and 24 months and 5 years (after 3 months blanking period), on or off antiarrhythmic drugs (AAD).
- Freedom from documented persistent atrial arrhythmia at 12 and 24 months and 5 years (after 3 months blanking period), on or off AAD.
- Freedom from DC cardioverted atrial arrhythmia at 12 and 24 months and 5 years (after 3 months blanking period), on or off AAD.
- Number of DC-cardioversions (after 3 months blanking period) and sustained atrial arrhythmia episodes at 12 and 24 months and 5 years.
- Freedom from accepted chronic atrial fibrillation at 12 and 24 months and 5 years.
- Freedom from re-ablation procedure at 12 and 24 months and 5 years.
- Change in AFEQT score between baseline and 24 months and between baseline and 5 years.

Primary safety endpoints:

- Peri- or postprocedural complications (vascular complication needing intervention, conduction disturbances requiring a pacemaker, gastroesophageal fistula, phrenic nerve damage, stroke or systemic embolism, PV stenosis, cardiac tamponade, anaphylactic reaction, pericarditis and death).

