### 3.7 Strategy for the procedure

According to standard clinical protocol and in accordance with international recommendations, after obtaining venous vascular access, a 10-polar catheter is placed in the coronary sinus and one transseptal puncture is performed. After the placement of a steerable sheath (Agilis™, Abbott, Abbott Park, IL), a multipolar mapping catheter PENTARAY™ or OCTARAY™ (Biosense Webster, Diamond Bar, CA, US) or Advisor™ HD Grid (Abbott, Abbott Park, IL) will be deployed in the LA.

The procedure will subsequently consist of two phases:

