## 5.0 ETHICAL ASPECTS

### 5.1 Risks and inconvenience

The duration of the procedure is expected to be approximately 60 minutes longer in the intervention group compared to the control group. However, the majority of complications related to AF ablation, are related to the transseptal puncture, which will be performed in both groups.

In the intervention group, more widespread ablation will take place, potentially increasing the risk of severe complications such as tamponade, stroke, coronary artery lesion, esophageal fistula, phrenic nerve palsy, and conduction disturbances requiring a pacemaker. These complications are rare and reported after less than <0.1% of procedures, including procedures with extensive ablation for PsAF. VOM ethanol ablation carries an increase in the risk of pericarditis and a very small risk (0.4%) of anaphylactic reaction.

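### Coronary artery lesion is the only severe complication flagged in section 5.1 that the primary safety endpoint does not name

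*Protocol*

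**What the plan says.** Section 3.5 of the Protocol defines the primary safety endpoint as complications during or after the procedure, followed by a bracketed list. Seven components come first: "vascular complication needing intervention, conduction disturbances requiring a pacemaker, gastroesophageal fistula, phrenic nerve damage, stroke or systemic embolism, PV stenosis, cardiac tamponade". The remaining three of the ten are death, pericarditis and anaphylactic reaction. The safety row of the Protocol overview gives the same list, ending "stroke or systemic embolism, pulmonary vein stenosis, cardiac tamponade, anaphylactic reaction, pericarditis and death". Neither list names a coronary event, and neither contains a term such as 'other' or 'including'.

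Section 5.1 describes the more widespread ablation in the intervention group as "potentially increasing the risk of severe complications such as tamponade, stroke, coronary artery lesion, esophageal fistula, phrenic nerve palsy", and adds conduction disturbance leading to a pacemaker. It then puts a ceiling of 0.1% of procedures on these events, in the sentence that opens "These complications are rare and reported after less than". It mentions pericarditis and anaphylactic reaction separately, as risks of the ethanol ablation.

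Section 3.2 foresees energy delivery close to these vessels ("radiofrequency should be preferred near coronary arteries"). It also sets out what each arm receives. Before randomization, in all patients: "If reconnection is present, re-PVI will be performed". After randomization: "patients in control group will undergo no further ablation".

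**The concern.** A safety endpoint in a trial of added ablation should count the harms that the protocol itself expects the added ablation may increase. Section 5.1 names those harms, and the endpoint picks up all but one of them by name.

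If a coronary lesion occurred, the protocol would not settle whether it is a safety endpoint event, so someone would have to decide after the event. Section 3.2 assigns outcome assessment to blinded personnel. However, section 3.12 leaves the investigator unblinded, and section 7.3 has the primary investigator and the study nurse record the data. The decision might therefore fall to someone who knows the allocation. Only the reported complication comparison is at stake. The AFEQT analysis and the sample size are not touched.

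**Working it through.** **Step 1. Match the two lists.** Left: every complication named in section 5.1. Right: the component in section 3.5 and the overview.

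| Section 5.1 | Safety endpoint component |
|---|---|
| Tamponade | Cardiac tamponade |
| Stroke | Stroke or systemic embolism |
| Esophageal fistula | Gastroesophageal fistula |
| Phrenic nerve palsy | Phrenic nerve damage |
| Conduction disturbance with pacemaker | Same |
| Coronary artery lesion | None named |
| Pericarditis (ethanol) | Same |
| Anaphylactic reaction (ethanol) | Same |

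Five of the six severe complications, and seven of all eight, are named. Coronary artery lesion is the only exception.

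**Step 2. Sort coronary lesions by how the list would treat them.**

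- Fatal, or leading to another listed event such as tamponade: counted through that other component.
- Needing intervention: counted only if the vascular component that opens the list includes coronary vessels. The term is not defined. Outside the two endpoint lists, 'vascular' as a separate word appears only in section 3.7 ("after obtaining venous vascular access"). That passage describes a procedural step and does not settle the meaning.
- Non-fatal, needing no intervention and leading to no other listed event: under no named component on any reading.

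**Step 3. Which arm.** Re-isolation precedes randomization, so a lesion from that step could fall in either arm. Only the intervention arm then has further lines, including ablation inside the coronary sinus where needed (section 3.7). The expected excess is therefore in the intervention arm.

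**Step 4. Size.** Inputs: 180 patients (section 3.4, power calculation), 1:1 allocation (section 3.12) and a ceiling of 0.1% (section 5.1). Arm size: 180 / 2 = 90. The expected count is 90 × rate, and the chance of at least one event is 1 − (1 − rate)^90.

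- Ceiling applied to each complication: 90 × 0.001 = 0.09 lesions of any kind; chance 1 − 0.999^90 = 8.6%.
- Ceiling applied to all six jointly, split equally (an assumption): 90 × 0.001/6 = 0.015; chance 1 − (1 − 0.001/6)^90 = 1.5%.

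The lesions left uncounted are a subset of these. The documents do not give their share, so the following shares are assumptions applied to the first reading:

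| Assumed uncounted share | Expected uncounted lesions | Chance of one or more |
|---|---|---|
| 25% | 90 × 0.00025 = 0.02 | 2.2% |
| 50% | 90 × 0.0005 = 0.05 | 4.4% |
| 75% | 90 × 0.00075 = 0.07 | 6.5% |

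All of these are upper values, because section 5.1 says the rate is below the ceiling. They hold only if that ceiling carries over to this arm.

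**The case against.** The strongest reply is that the vascular component already covers the cases that matter. In ordinary language a coronary lesion needing intervention is a vascular complication needing intervention, and a lesion with no clinical consequence may not be what section 5.1 means by severe. Part of this stands. A reader might infer from the lists that coronary lesions have no counterpart in the endpoint at all. The documents do not support that, because the undefined term can be read to include them. What remains is an ambiguity for one group of lesions and a definite gap for a narrower one. A consequence threshold may be deliberate, but phrenic nerve damage and pericarditis are listed without one.

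A second reply is that section 5.1 discloses risks by example and section 3.5 defines an endpoint, so no contradiction arises. That is fair: nothing obliges every disclosed risk to be a component, and the protocol does not say that the bracket is exhaustive. For that reason the point is put as 'not a named component' and not as 'excluded'.

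A third reply is that the events are too rare to matter. Their rarity makes the point minor, but it does not explain the omission: the other five severe complications carry the same stated ceiling and are all listed.

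A fourth reply is that such definitions belong in the statistical analysis plan or the eCRF. This holds for the detailed wording of a definition. The component list, however, is fixed in the protocol itself, in two places.

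A reader might also infer that these events would be lost. The documents do not show that: sections 7.2, 7.4 and 7.5 provide for eCRFs, source records and the keeping of adverse event reports. Planned follow-up in section 3.10 contains no coronary imaging, so a silent lesion might go undetected even if it were named.

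**Conclusion.** The point holds as a minor correction. Coronary artery lesion is the only severe complication tied to the intervention in section 5.1 that the primary safety endpoint does not name. Lesions needing intervention are counted or not depending on how one undefined term is read. Non-fatal lesions that need no intervention and cause no other listed event fall under no named component.

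The expected size is at most about 0.09 lesions of any kind in the intervention arm, with about a 9% chance of seeing one or more. This assumes that the ceiling in section 5.1 applies to each complication and to this arm. That second assumption is not secure, because the ceiling comes from a cited source on AF ablation and section 5.1 treats the ethanol risks separately. The uncounted part is smaller still, and its share is not known from the documents.

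The expected direction of any omission favours the intervention. It would be too strong to say that the safety comparison is materially biased, or that control patients cannot have such a lesion. The numbers do not support the first, and re-isolation in both arms rules out the second.

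**What to change.** Reconcile the safety row of the Protocol overview and section 3.5 with section 5.1:

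- Name coronary artery lesion, as the investigators define it, as a component in both lists.
- Capture it as an item in the eCRF.
- State whether the vascular component means access-site events only or also coronary events, so that no event is counted twice.

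The cost is one term in two lists, one clarifying phrase and one eCRF item, with no change to the sample size or the efficacy analysis. The downside is that the reported complication rate may become slightly less favourable to the intervention.

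### The safety endpoint list names gastroesophageal fistula while section 5.1 warns of esophageal fistula; the two lists should be reconciled, and any pooled safety count shown with and without pericarditis

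*Protocol*

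**What the plan says.** Protocol 3.5 places one bullet under the heading "Primary safety endpoints". The bullet gives peri- or postprocedural complications, with the qualifying events in brackets. The fistula component stands in the run "conduction disturbances requiring a pacemaker, gastroesophageal fistula, phrenic nerve damage, stroke or systemic embolism". The Protocol overview repeats it: "Peri- or postprocedural complications (vascular complication needing intervention, conduction disturbances requiring a pacemaker, gastroesophageal fistula, phrenic nerve damage".

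Section 5.1 says that the more widespread ablation in the intervention group may raise the risk of severe complications, and names them as "tamponade, stroke, coronary artery lesion, esophageal fistula, phrenic nerve palsy, and conduction disturbances requiring a pacemaker". It puts these below 0.1% of procedures. It adds that "VOM ethanol ablation carries an increase in the risk of pericarditis", without a rate, and gives 0.4% for anaphylactic reaction.

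Two of the ten components in 3.5 carry a severity condition: "vascular complication needing intervention, conduction disturbances requiring a pacemaker". Pericarditis carries none and stands at the end of the list: "PV stenosis, cardiac tamponade, anaphylactic reaction, pericarditis and death". Section 3.2 confines VOM ethanol to the intervention group.

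**The concern.** An endpoint list decides which events are counted. Section 7.2 says the case report forms will be built to capture what the protocol outlines, so a form that follows 3.5 would offer a field for gastroesophageal fistula. Taken at face value, that term means a connection between stomach and esophagus. The broader term in 5.1 also covers a fistula from the esophagus to another structure. An assessor who applies 3.5 strictly could leave out an event that 5.1 treats as one of the gravest risks of the added ablation. Both endpoint lists use the narrower term, so neither names the harm as 5.1 does.

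The second question is how the list behaves if it is counted as one endpoint. The component expected to differ between arms, pericarditis, has no severity condition and would count the same as death. An excess made up largely of pericarditis could then be read as a general excess of serious complications.

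**Working it through.** **Step 1: set the two lists side by side.**

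| Severe complication in 5.1 | Counterpart in the 3.5 and overview lists |
|---|---|
| Tamponade | Present |
| Stroke | Present (with systemic embolism) |
| Coronary artery lesion | Not named |
| Esophageal fistula | Different term: gastroesophageal fistula |
| Phrenic nerve palsy | Present (as phrenic nerve damage) |
| Conduction disturbance requiring a pacemaker | Present |

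Four of six match, one is under a different term and one is absent. The documents define neither fistula term. The comparison therefore shows a conflict between sections and does not prove that the authors meant to exclude anything.

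**Step 2: what a pooled count would contain.** The protocol states no rate, power or sample size for the safety endpoint, so there is no figure to reproduce. The following is an illustration for the intervention arm.

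Inputs:
- Patients: 180 randomized 1:1 (3.4 Power calculation, 3.12), so 180 / 2 = 90.
- Severe complications: below 0.1% (5.1). The text does not say whether this is each or all together, so both are used, at the upper limit.
- Anaphylaxis: 0.4% (5.1).
- Pericarditis: not given. Assumed range 1%, 2%, 5% and 10%.

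Expected events = 90 × rate:
- Severe, 0.1% for all together: 90 × 0.001 = 0.09.
- Severe, 0.1% for each of the six in 5.1: 90 × 0.006 = 0.54.
- Severe, 0.1% for each of the five left after dropping coronary artery lesion, which is not a listed component: 90 × 0.005 = 0.45.
- Anaphylaxis: 90 × 0.004 = 0.36.

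Share of pericarditis = pericarditis / (pericarditis + severe + anaphylaxis):

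| Assumed rate | Pericarditis events | Severe 0.54 | Severe 0.45 | Severe 0.09 |
|---|---|---|---|---|
| 1% | 0.9 | 0.9/1.80 = 50% | 0.9/1.71 = 53% | 0.9/1.35 = 67% |
| 2% | 1.8 | 1.8/2.70 = 67% | 1.8/2.61 = 69% | 1.8/2.25 = 80% |
| 5% | 4.5 | 4.5/5.40 = 83% | 4.5/5.31 = 85% | 4.5/4.95 = 91% |
| 10% | 9.0 | 9.0/9.90 = 91% | 9.0/9.81 = 92% | 9.0/9.45 = 95% |

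**Step 3: how fragile this is.** Vascular complications, PV stenosis, systemic embolism and death have no stated rate and are left out of the denominator; including them would lower every share. With 0.45 severe events and 0.36 anaphylaxis (0.81 together), pericarditis falls below half once the unrated components add more than:
- 0.9 - 0.81 = 0.09 events (0.1% of 90) at an assumed 1%;
- 1.8 - 0.81 = 0.99 events (1.1%) at 2%;
- 4.5 - 0.81 = 3.69 events (4.1%) at 5%.

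At the low end of the range the majority is therefore not secure.

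**The case against.** On the fistula, the best reply is that this is a slip of terminology. Section 5.1 shows that the authors have esophageal fistula after ablation in mind, and a sensible assessor would record one. That is probably true, and it limits the practical risk. It does not make 3.5 and 5.1 agree, and a safety endpoint should not depend on the assessor's charity. It could likewise be said that a coronary lesion falls under vascular complications needing intervention; the protocol does not say so.

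On pericarditis, a reader might infer that the trial has a single composite safety endpoint that pericarditis will drive. The documents do not support that. The headings are plural, nothing calls the list a composite, and 3.11 gives no pooling rule for safety. The events may well be reported one by one, and how they are combined can properly be left to an analysis plan that is not shown here.

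A reader might also infer that pericarditis would make serious harms invisible. That goes too far. The components are itemised, and the Data update section requires adverse events to be documented. With well under one expected severe event of the rated kinds in 90 patients, no comparison of those events between arms would be informative however pericarditis is handled.

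Finally, it is tempting to ask for a severity threshold, or for a main count that leaves pericarditis out. Eight of the ten components have no threshold, phrenic nerve damage and PV stenosis among them, so pericarditis is not a lone exception. Removing it would take a predicted harm of the intervention out of the headline comparison. Listing it without restriction is a defensible, conservative choice, and this objection stands.

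**Conclusion.** The inconsistency is real: the safety lists in 3.5 and the overview use a fistula term that, read literally, does not match the harm named in 5.1, and they do not name coronary artery lesion. This is a narrow defect in an operative endpoint definition. It does not touch the primary efficacy analysis.

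The pericarditis point holds only conditionally. If the list is analysed as one count, pericarditis could supply much of it: about half or more of the rated events at an assumed 1-10%. That rests on a rate the protocol does not give, on 0.1% taken as an upper limit, and on leaving out components with no stated rate. It supports transparent reporting and does not support removing or restricting pericarditis.

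**What to change.** In 3.5, the overview and 5.1, use one term that covers any fistula involving the esophagus, and carry it into the case report form. In the same amendment, reconcile coronary artery lesion: add it to the safety list, or state which listed component covers it.

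Keep pericarditis in the endpoint. State that every component will be reported by arm and, if a pooled count is also given, show it both with and without pericarditis.

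The cost is a small wording amendment and one extra table row. No change to sample size or to the primary analysis follows.
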